#### 3.3. Antibiotics Disposal and Administration

Once a subject is consented and randomized, the appropriate antibiotics according to group assignment will be dispensed by the regular hospital pharmacists after order is placed in EPIC (as part of standard procedure at UTMB). Both drugs are standard of care at UTMB. This is a pragmatic/comparative effectiveness of two standard of care therapies. Regular hospital pharmacy currently stores and disposes the drugs and subject's insurance will be responsible for paying for either antibiotic, as any other subject not in the study. Floor nurses will be administering antibiotics. Research staff will be checking medication administration record (MAR) in EPiC for compliance to the research protocol; if an antibiotic is withheld for any reason the staff will inform the PI and report it as a protocol deviation which may potentially affect the integrity of the data for that subject.

The subject will be included in the analysis by intent-to-treat once the assigned antibiotics are dispensed from inpatient pharmacy and sequential number posted on the subject specific randomization form.

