#### 3.1 Screening, Recruitment and Consenting:

Under the direction of the PI, trained research staff will be available 24/7 to screen and consent subjects according to study protocol. Medical records of all potential subjects with a diagnosis of PPROM will be reviewed and those who satisfy inclusion and exclusion criteria will be approached and a written informed consent will be obtained. A screening log will be used to track all subjects approached for the study. Potential subjects may be patients of the investigators.

Subjects will be enrolled at the time of admission to labor and delivery (L&D) or thereafter. Subjects will be recruited, enrolled and consented in a private room in labor and delivery or antepartum units in order to respect the privacy of potential subjects. Subjects will be given all the time needed in order to fully understand and read the consent forms. All questions will be fully answered. If needed, a certified language interpreter will be available and Spanish consents will be used as appropriate. Women will only be randomized on our labor and delivery or antepartum units when the decision to initiate antibiotics is made, AND they continue to be eligible (using a randomization screen).

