#### 3.2 Randomization

A confidential computer-generated simple randomization scheme (using STATA 14, Dallas, Tx) will be prepared and provided on an ongoing basis to our study coordinator. A randomization log with group assignment, subject name and medical record number will be used to track the randomization process. Across multi-sites, randomization is centralized. UTMB perinatal research division synchronizes randomization assignment schedule by increments of blocks of 10 as enrollment is ongoing.

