#### 3.6. Withdrawals

Subjects who withdraw from the study after randomization will be excluded from further follow-up. Outcomes ascertained up until the time of withdrawal will be reported in an intent to treat fashion. Those who withdraw prior to determining the primary outcome will be accounted for by randomizing an equal number of additional subjects.

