# 12-Potential benefits:

In the background of erythromycin nationwide shortage, this will be the first level 1 trial to show that azithromycin may be equivalent to erythromycin in delaying delivery in patients with PPROM. This study may show for the first time that current alternative practice with azithromycin is as effective as erythromycin but with less adverse effects, less costly and easy administration.

13-**Statistical approach:** Analysis will be performed by intent to treat. Univariable analysis (such as t-test, Mann-Whitney or Chi-square) will be used for descriptive statistics such as patient demographics and assessment of primary outcome. Multivariable logistic analysis will be used to account for potential confounding variables. Sample size was calculated using a noninferiority trial design. Azithromycin will be tested against erythromycin for PPROM. The primary outcome will be the proportion of subjects undelivered

by day 7. For the sample size calculation, it is assumed the proportion undelivered in the erythromycin group would be 70% (pi = 0.7) based on Haas et al study. We considered that a difference in undelivered rate as large as 15% in favor of erythromycin would allow azithromycin to be non-inferior (delta = 0.15). This study will use 80% power to confirm non-inferiority and a one-sided confidence level of 97.5%.

Estimated sample size for two-sample comparison of proportions (non-inferiority)

Null hypothesis: p2 - p1 � delta (inferior), where:

pi (entered in command) is the overall proportion of participants expected to experience the outcome if the treatments are non-inferior, and delta is the smallest change in proportions between groups (p2 - p1) which would still be clinically important.

Alternative hypothesis: p2 - p1 < delta (non-inferior)

Note: a non-inferiority analysis is one-sided.

```
Assumptions:

power = 0.8000

alpha = 0.0250 (one-sided)

pi = 0.7000

delta = 0.1500

estimated required sample size (per group) = 147
```

The total estimated sample size is 294. Assuming 10% loss to follow, this study proposes a total of 324 subjects will be needed to complete the study. The STAT 14 (Dallas, Tx) will be used for statistical computations. This trial will be registered with Clinical Trials Register (Clinicaltrials.gov), before recruitment is initiated and after IRB approval."

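### The plan states intent-to-treat, but it admits women at dispensing and stops follow-up at withdrawal, so some randomised women drop out of the primary comparison

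*Combined protocol and SAP*

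**What the plan says.** Section 13 (Statistical approach) gives the principle in one sentence, "Analysis will be performed by intent to treat", and does not define the analysis set. The only entry rule is in section 3.3: "The subject will be included in the analysis by intent-to-treat once the assigned antibiotics are dispensed from inpatient pharmacy", together with the posting of a sequential number on the randomisation form. The same section places dispensing after consent and randomisation.

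Section 3.6 covers withdrawal in three sentences. The first ends the follow-up of any woman who leaves the trial once she has been allocated. The second deals with data gathered before she left: "Outcomes ascertained up until the time of withdrawal will be reported in an intent to treat fashion". The last concerns women whose day-7 status is still unknown when they leave, and its remedy is replacement: "Those who withdraw prior to determining the primary outcome will be accounted for by randomizing an equal number of additional subjects".

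Section 13 also provides for attrition: "Assuming 10% loss to follow, this study proposes a total of 324 subjects will be needed to complete the study". No section says how a randomised woman with unknown day-7 status is counted, and none plans a sensitivity analysis for such women.

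**The concern.** Intent-to-treat protects the comparison because every randomised woman is counted in the arm she was assigned to. Two groups lose that protection here:

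1. **Randomised but not dispensed.** This includes a woman who delivers or is withdrawn between the two steps.
2. **Withdrawn while still pregnant before day 7.** Her outcome is not yet known, follow-up stops, and another woman is randomised in her place. Replacement restores the count but not the randomised comparison.

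A woman who delivers and then withdraws is not affected, because her outcome is already known and is kept. A withheld antibiotic is a protocol deviation, not a withdrawal. Outcome review is masked (section 3.4) and delivery is an objective event, so the issue is who is counted, not how the outcome is judged.

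The trial's conclusion rests on a 15-point margin with 147 women per arm. A few exclusions related to both arm and outcome could raise the chance of a false non-inferiority claim or lower the power. Loss could differ by arm: no masking of treatment is described, the regimens differ in number of doses, and section 7.3 lists nausea and vomiting at 25% for erythromycin against 3% for azithromycin.

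**Working it through.** **Inputs (section 13).** Proportion undelivered at day 7: 0.70. Margin: 0.15. One-sided alpha: 0.025. Power: 0.80. The plan gives 147 per group, 294 in total, and 324 after the 10% allowance.

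**The plan's own figures.** n = 2 × 0.7 × 0.3 × (1.96 + 0.8416)² / 0.15² = 146.5, rounded up to 147 per group, or 294. Then 294 × 1.10 = 323.4, rounded up to 324. Both are reproduced. The allowance is 324 − 294 = 30 women.

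**Effect of exclusions.** The documents give no exclusion rate, so 1%, 2% and 5% are assumptions. At 147 per arm, 1% is about 1.5 women and 2% about 3. Let *f* be the fraction lost from an arm with true rate *p*, and *q* the share of lost women who would have reached day 7 undelivered. The rate among those analysed is (p − f·q)/(1 − f). Non-inferiority is declared when the lower two-sided 95% Wald limit for azithromycin minus erythromycin exceeds −0.15. Probabilities are exact binomial with 147 analysed per arm.

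With no loss, false non-inferiority (true rates 70% erythromycin, 55% azithromycin) is 2.4%, and power (both 70%) is 80.2%.

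| Loss in one arm only | 1% | 2% | 5% |
|---|---|---|---|
| Erythromycin, all would have reached day 7 (q = 1): rate analysed | 0.697 | 0.694 | 0.684 |
| – false non-inferiority | 2.7% | 3.1% | 4.4% |
| Azithromycin, all would have delivered early (q = 0): rate analysed | 0.556 | 0.561 | 0.579 |
| – false non-inferiority | 3.0% | 3.8% | 7.3% |
| Erythromycin, all would have delivered early (q = 0): rate analysed | 0.707 | 0.714 | 0.737 |
| – power | 76.6% | 72.6% | 58.0% |

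Example: 2% azithromycin loss with q = 0 gives 0.55/0.98 = 0.561.

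**Milder patterns.**

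- Loss unrelated to outcome (q equal to the arm's own rate): error stays at 2.4%.
- Equal loss of early deliverers from both arms at 1–2%: error 2.1–2.2%, power 81%.
- One-arm loss at 1–2% with less extreme outcomes: error 2.5–2.7% if 85% of lost erythromycin women would have reached day 7, and 2.7–3.0% if 27.5% of lost azithromycin women would have.

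**Worst-case bound for missing status.** Take 162 per arm and 70% observed in each. Count missing azithromycin women as delivered and missing erythromycin women as undelivered. At 5% missing per arm:

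- Erythromycin: 0.7 × 0.95 + 0.05 = 0.715. Azithromycin: 0.7 × 0.95 = 0.665. Difference: 0.050.
- Upper 97.5% limit: 0.050 + 1.96 × √[(0.715 × 0.285 + 0.665 × 0.335)/162] = 0.151.

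The limit is 0.100 with none missing and 0.120 at 2%. It reaches the 0.15 margin at about 5% missing per arm, half the plan's own 10% allowance.

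**Cost of the fix.** Suppose a fraction *f* of erythromycin women are not dispensed it, receive azithromycin and have its 55% rate. Counting them in their assigned arm gives an erythromycin rate of (1 − f) × 0.70 + f × 0.55. For f = 1%, 2%, 5% and 10% this is 0.6985, 0.6970, 0.6925 and 0.6850, with false non-inferiority of 2.5%, 2.7%, 3.2% and 4.3%.

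**The case against.** The strongest reply is that the text is ambiguous rather than wrong. The dispensing sentence may only be meant to fix the point of enrolment, and section 3.6 never says outright that a withdrawn woman leaves the denominator. That is fair as to intent. But the sentence governs inclusion in the analysis and nothing else defines the set. A woman who withdraws undelivered before day 7 cannot enter a day-7 proportion when follow-up has stopped and no rule gives her a status.

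The second reply is that few women are affected, and this largely stands. Section 3.1 says: "Women will only be randomized on our labor and delivery or antepartum units when the decision to initiate antibiotics is made". Eligibility is rechecked at that point, both regimens come through the ordinary hospital pharmacy, and the endpoint is only a week away.

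The third is that the larger figures need one-arm loss with a uniform outcome. This also stands:

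- Women who deliver between randomisation and dispensing do so before the assigned drug can act, so their loss should be balanced unless dispensing itself depends on arm.
- Women who withdraw early are by definition still pregnant, so the worst error case describes them poorly.
- Non-dispensing caused only by the erythromycin shortage (section 1) would probably be unrelated to outcome.

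Finally, abstraction after withdrawal depends on consent terms that were not available for this review, so it may already be permitted or may be restricted.

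**Conclusion.** The concern holds. Followed literally, the plan drops two groups of randomised women while calling the analysis intent-to-treat, and it has no rule for missing day-7 status. The numbers are probably small, the bias could run either way, and there is none if loss is unrelated to outcome. At an assumed 1–2% loss from one arm, false non-inferiority is at most 3.0–3.8% against 2.4%, and power is at lowest 76.6–72.6% against 80.2%. The 5% figures (7.3% error, 58.0% power) are extremes with no documented rate behind them.

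The case for change rests on the definition of the analysis set, not on these illustrations. The sponsor should make the change. Confidence is medium, because the size of the problem cannot be learned from the documents.

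**What to change.** - Define the primary analysis set as all randomised women in their assigned arm, whether or not drug was dispensed.
- Continue abstracting delivery date and time from the medical record after withdrawal (section 3.7 already lists these items), unless consent for data use is withdrawn.
- State that replacing a withdrawn woman does not remove her from the analysis set, and say whether replacements come from the 30 women above 294 or are added to the 324.
- Report non-dispensing, withdrawal and missing day-7 status by arm, with a sensitivity analysis for missing status. Section 3.2 already provides for "A randomization log with group assignment", and section 3.3 for deviation reports, so much of this information would exist.
- Report a per-protocol analysis alongside, using the medication administration record already checked under section 3.3, and discuss any disagreement.

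The cost is protocol wording, one sensitivity analysis and one per-protocol analysis, mostly on data already abstracted. A few outcomes may still be missing. Counting women who did not receive their assigned drug can pull the arms together slightly (2.5–2.7% error against 2.4% at 1–2% cross-over), which is the reason for the per-protocol analysis. That set is not fully randomised either, so neither analysis should be read alone.

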#### **3.4.** Baseline Procedures

Routine PPROM care will be provided by the subjects' clinical providers.

Trained and experienced research staff will be responsible for all research data abstraction.

The PI will review and validate the diagnosis for all subjects identified to have the primary outcomes. These reviews will be conducted masked to treatment group. If there is uncertainty, a will review the chart, discuss with the co-investigators as needed and make a final determination regarding the outcome.

Maternal and neonatal outcomes will be assessed in the hospital following the delivery (on an ongoing basis until discharge).

Several data collection forms will be used during these processes. Data on these forms, devoid of personal identifiers, will be securely stored at our perinatal research division.

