# 4- Study procedures:

Eligible subjects will be approached, and those who consent will be randomized to one of the two groups below in a 1-to-1 allocation.

- Erythromycin group: Ampicillin 2 gm IV every 6 hours first 2 days followed by amoxicillin 250 mg PO every 8 hours for next 5 days with erythromycin 250 mg IV every 6 hours for first 2 days followed by 500 mg PO every 8 hours for next 5 days (standard of care at UTMB).
- Azithromycin group: Ampicillin 2 gm IV every 6 hours first 2 days followed by amoxicillin 500 mg PO every 8 hours for next 5 days with azithromycin 1 gm PO once at randomization (Standard of care at UTMB).
   Both groups receive a total of 7 days of antibiotics as per standard of care at

The remaining standard of care will be the same for both groups concerning the management of PPROM according to NICHD/ACOG guidelines including GBS prophylaxis.

GBS chemoprophylaxis is beyond the scope of this trial, since we are randomizing the portion of macrolides only and not the Ampicillin portion that actually covers GBS. As noted, this regimen of intravenous ampicillin/ amoxicillin, is standard on both interventions and covers GBS. GBS cultures and GBS treatment is left per providers' discretion beyond our intervention period (7 days of latency antibiotics). In addition, drug adverse effects profiles between the two will be assessed in a post treatment subject survey. Subjects will complete a survey before being discharged from the hospital after receiving the assigned antibiotic regimen. Any questions will be answered and sufficient time will be given for the subject to fill the survey. Data will be collected retrospectively from EPIC EMR:

- Time of initiation of antibiotics to delivery.
- Maternal outcomes: chorioamnionitis, postpartum infectious morbidity, placental abruption
- Route of delivery

UTMB.

- Gestational age at delivery
- Adverse events: Allergic reactions (anaphylaxis, angioedema, skin rashes including Stevens Johnson and Toxic Epidermal necrolysis), GI symptoms (vomiting, diarrhea, constipation, ileus)
- Neonatal outcomes: perinatal death, need for oxygen supplementation (not intubated), ventilation support (intubated), necrotizing enterocolitis (NEC) stage 2 or 3, duration of ventilator support (intubated), NICU days and neonatal infection/sepsis, individually and as a composite.

Both survey forms and data forms are attached with protocol application.

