# 3.7 Outcomes

# Primary outcome:

• Proportion of undelivered subjects at day 7 from the diagnosis of PPROM

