#### **10-Subject Safety and Data Monitoring:**

The collaborators and research coordinator will be responsible for monitoring the safety of this study. The report will include participant demographics, expected versus actual recruitment rates, summary of any quality assurance or regulatory issues, summary of adverse events (AEs) or serious adverse events (SAEs) which may have occurred, and any changes in the protocol as a result of these issues. This report will be prepared yearly and be sent to the PI's. The collaborators and research coordinator will monitor for adherence to consent procedures, inclusion and exclusion criteria, valid abstraction, correct entry, timeliness and responsiveness to data queries. Data collection will be identified with a participant ID number. Data will be collected and stored with the participant ID code only. The master enrollment log linking subject identifiers with study ID numbers will be kept in a password-protected database. Several data collection forms will be used. Data on these forms devoid of personal identifiers will be securely stored at our perinatal research division. The research coordinator and PIs will be available to monitor the data and correct any discrepancies based on source documents if needed.

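### Outcome validation is written to cover only women recorded as undelivered at day 7, and no procedure secures the masking claimed for it

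*Combined protocol and SAP*

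**What the plan says.** Section 3.7 defines the primary outcome as "Proportion of undelivered subjects at day 7 from the diagnosis of PPROM". To have the outcome is therefore to be still pregnant.

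Section 3.4 sets the validation rule: "The PI will review and validate the diagnosis for all subjects identified to have the primary outcomes". It adds: "These reviews will be conducted masked to treatment group". Uncertain cases go to a further chart review and a final decision on the outcome. The role of the person who does this is not legible in the text available. No matching review is described for women recorded as delivered before day 7.

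Other sections bear on the masking:

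- Section 3.3: "if an antibiotic is withheld for any reason the staff will inform the PI and report it as a protocol deviation".
- Section 3.1: "Potential subjects may be patients of the investigators".
- Section 4 gives one arm "amoxicillin 250 mg PO every 8 hours for next 5 days with erythromycin 250 mg IV every 6 hours for first 2 days" and the other "amoxicillin 500 mg PO every 8 hours for next 5 days with azithromycin 1 gm PO once at randomization". No blinding of treatment is described.
- Section 10: "The research coordinator and PIs will be available to monitor the data and correct any discrepancies based on source documents if needed". No masking is mentioned there.

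**The concern.** A check applied to one outcome state can correct errors in one direction only. Here it can turn a recorded success into a failure. A woman wrongly recorded as delivered before day 7 stays a failure unless something else catches the error. In a non-inferiority comparison, uncorrected misclassification that is equal in the two arms shrinks the observed difference, which favours a conclusion of non-inferiority. If the person reclassifying knows the arm, the difference can move either way.

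Masking is the safeguard against that second problem, and the plan states it without saying how it is achieved. The same role that validates outcomes also receives reports about antibiotic administration, in a trial where the arms receive visibly different drugs.

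**Working it through.** **Plan's own figure.** Inputs from section 13: 70% undelivered, margin 0.15, one-sided alpha 0.025, power 80%.

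n per arm = (1.960 + 0.842)² × 2 × 0.70 × 0.30 / 0.15² = 146.5, rounded up to 147, or 294 in total. This reproduces the plan.

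**Women covered by the check.** 0.70 × 294 = 205.8, about 206. Not covered: 294 − 206 = 88.

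**What a withheld-antibiotic report reveals.** Section 3.3 refers to any antibiotic, so all scheduled doses in section 4 count.

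- Ampicillin every 6 h for 2 days: 8 doses in each arm.
- Amoxicillin every 8 h for 5 days: 15 doses in each arm.
- Erythromycin: 8 IV + 15 oral = 23 doses. Azithromycin: 1 dose.
- Totals: 8 + 15 + 23 = 46 against 8 + 15 + 1 = 24.

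Let q be the chance that any one dose is withheld. The documents give no rate, so q is an assumption. P(at least one report) = 1 − (1 − q)^doses. With 1:1 allocation, the chance that a woman with a report is in the erythromycin arm is P(E) / [P(E) + P(A)].

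| q | Erythromycin, 46 doses | Azithromycin, 24 doses | Chance of erythromycin, drug not named |
|---|---|---|---|
| 0.5% | 20.6% | 11.3% | 65% |
| 1% | 37.0% | 21.4% | 63% |
| 2% | 60.5% | 38.4% | 61% |

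If the drug is not named, a report is a weak clue (61–65% against 50% by chance). If it names the macrolide, it identifies the arm. Macrolide reports alone would arise for 1 − (1 − q)^23 = 11% to 37% of erythromycin women, against 0.5% to 2% of azithromycin women.

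**Sensitivity of the test.** This is an illustration, and every error rate is assumed. Take 147 per arm and true rates of 0.70 and 0.55, so the true difference equals the margin. The chance of wrongly declaring non-inferiority is Φ[(0.15 − d)/SE − 1.96]. Here d is the difference in recorded rates and SE = √{[pE(1 − pE) + pA(1 − pA)]/147}. Let Se be the share of truly undelivered women recorded as such, and Sp the share of delivered women recorded as such. A check of recorded successes that catches every false one sets Sp = 1 and leaves Se as it was, so d = 0.15 × Se.

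| Equal error in both arms | One-sided type I error |
|---|---|
| Both states checked | 0.025 |
| Successes only, Se 0.98 | 0.028 |
| Successes only, Se 0.95 | 0.034 |
| Successes only, Se 0.90 | 0.045 |
| No check, Se = Sp = 0.98 | 0.032 |
| No check, Se = Sp = 0.95 | 0.045 |

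Worked line for Se 0.98: the recorded rates are 0.686 and 0.539, d = 0.147, SE = 0.0562, and Φ(0.003/0.0562 − 1.96) = 0.028.

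If reclassification lowers the erythromycin rate alone by 1, 2, 3 or 5 points (about 1.5, 3, 4 or 7 of 147 women), type I error is 0.037, 0.054, 0.077 or 0.140. In the other direction, with both true rates at 0.70, lowering the azithromycin rate alone by 2 points reduces power from 0.80 to 0.67.

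**The case against.** The strongest reply is that day-7 status compares two recorded times, so there is little to adjudicate, and removing a false success corrects an error. Most of this stands. At equal assumed error rates, checking successes only is better than no check (0.028 against 0.032; 0.034 against 0.045). It is not complete, because section 3.4 itself foresees uncertainty about the outcome. Section 3.7 also lists women undelivered at day 7 of admission, although the primary outcome counts from diagnosis.

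Four stronger readings are tempting, and the documents do not support them.

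- *The masking fails.* Open-label treatment with masked outcome review is coherent. Section 3.3 does not say that the report names the drug, and it concerns only women with a withheld dose. Section 3.1 says that subjects may be patients of the investigators, not that the PI reviews her or his own. The PI may differ by site, and uncertain cases go to a person whose role cannot be read.
- *All corrections run one way, and 88 women are never checked.* This is true of the section 3.4 step only. Section 10 provides for monitoring of abstraction and entry, and for correction from source documents in either direction.
- *PPROM is re-judged after randomisation in women with a good outcome.* The word diagnosis in section 3.4 invites this reading. But the paragraph ends with a decision on the outcome, and nothing says that a woman in whom PPROM is doubted loses her outcome or is excluded.
- *The difference shifts by 3.5 points.* That is 5% of 70%, and the 5% excess of overturned records in one arm has no source in the plan.

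**Conclusion.** The point holds in limited form. As written, the systematic outcome check reaches only women recorded as undelivered, about 206 of 294 on the plan's 70%, and that step can only turn successes into failures. Masking of the check is asserted without a procedure and is vulnerable for some women, chiefly where a withheld-dose report names the drug or an investigator has treated the woman.

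The documents do not allow the bias to be computed. For an endpoint based on dates it should be small. Under the assumed equal error rates, type I error rises from 0.025 to between 0.028 and 0.045. Serious distortion would need reclassification that depends on arm; about 3 of 147 women in the erythromycin arm alone would take it to 0.054. Nothing in the plan shows that this would occur. The sample size is unaffected. This is an inexpensive improvement to a stated one-sided rule, not a flaw that undermines the trial.

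**What to change.** Replace the validation rule in section 3.4:

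1. Derive day-7 status for every randomised woman from the recorded date and time of PPROM diagnosis and of delivery.
2. Apply any manual check, such as for missing dates or cases near the cut-off, to both outcome states alike.
3. Have that check done from an extract without drug or medication administration record data, by an existing investigator who does not receive the withheld-dose reports and is not treating the woman.
4. State that the review confirms the outcome and does not re-judge the PPROM entry diagnosis after randomisation.

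The cost is a change of protocol wording, the re-routing of one notification and slightly more checking of dates. Delivery date and time are already on the section 3.7 data list; the date and time of PPROM diagnosis should be added to it if the data forms do not already record them.
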